- To evaluate the additive effect of either quantitative or qualitative assessment of Tc 99m tilmanocept imaging to the other at baseline and change from baseline to 5 weeks \pm 1 week to predict clinical response or non-response following a change in anti-TNF α therapy.
- To evaluate the correlation of changes in TUV_{global} obtained before initiation of anti-TNFα therapy and at 5 weeks ± 1 week following a change in therapy with changes in composite clinical assessments and their constituent parameters at 12 and/or 24 weeks.
- To evaluate the correlation of changes in TUV_{global} obtained before initiation of anti-TNF α therapy and at 5 weeks ± 1 week following a change in therapy with changes in clinical assessments at 12 and/or 24 weeks for specific anti-TNF α bDMARD agents.
- To evaluate the ability of changes in TUV_{global} obtained before initiation of anti-TNF α therapy and at 12 weeks ± 1 week following change in therapy to accurately predict a clinical response or non-response at 24 weeks.
- To evaluate the correlation of changes with TUV_{global} and changes in clinical RA assessments as a means to monitor therapy.
- To evaluate sensitivity and specificity in patient subgroups.

• To evaluate the safety of IV-administered tilmanocept radiolabeled with Tc 99m.

The statistical endpoints that address these objectives are defined in Section 4 (efficacy) and Section 5 (safety). Refer to Section 2.2.1 for subgroup definitions and considerations.

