The Kendall rank correlation between $\Delta TUV_{global[5w]}$ with $\Delta CDAI_{12w}$ and $\Delta CDAI_{24w}$ will be computed and a 95% confidence interval for its value will be computed using Fisher's Z-transformation. Similarly, the Kendall rank correlation between $\Delta TUV_{global[5w]}$ with changes from baseline in DAS28 and in each of the ACR Response Criteria components at weeks 12 and 24 will be computed and a 95% confidence interval for its value will be computed using Fisher's Z-transformation. The marginal distributions of the variables will be characterized with the mean, standard deviation, and the number of data pairs.

The additive effect of either quantitative or qualitative assessment of Tc 99m tilmanocept imaging will be assessed with a generalized linear mixed model with the logit link function. The patient's response status will be used as the response variable. Fixed model terms for the quantitative and qualitative plus quantitative assessments will be used. The quantitative assessment will be based on $\Delta TUV_{global[5w]}$ bucketing. Random terms will be fit for the subject and reader within subject using the variance component model. A table displaying the partial hypothesis tests (Type 3 test) for the fixed effects will be displayed.

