STATKING Clinical Services (DD-MMM-YYYY)

Source Program: xxxxxx.sas

Table format is repeated for each reader. Entire table (all parts) is repeated for the PP population (table 34).

Table 35. Summary of Generalized Linear Mixed Model to Asses the Additive Effect of either Quantitative or Qualitative Assessment of Tc 99m Tilmanocept Imaging on Patient Response Status at Week 12 Navidea Biopharmaceuticals - Study No. NAV3-33

ITD Population (N=xxx)

Model Termª	Parameter Estimate ^b	Standard Error	95% Confidence Limits	p-value ^c
Quantitative Imaging Assessment	xxx.xxx	****	(xxx.xxx, xxx.xxx)	x.xxxx
Qualitative plus Quantitative Imaging Assessment	xxx.xxx	****	(xxx.xxx, xxx.xxx)	x.xxxx

^a Indicator variable for prediction of "Improved" compared to the reference category of "Not Improved."

^b Estimate calculated from a generalized linear mixed model with the logit link function with patient response status as the response variable, fixed terms for quantitative and qualitative plus quantitative imaging assessment, and random terms for subject and reader within subject using a variance component model.

 $^{\circ}$ Based on a two-sided t-test.

STATKING Clinical Services (DD-MMM-YYYY) Source Program: xxxxxx.sas

Table is repeated for the PP population (table 36) and for tables 37 – 38.

Page x of y

Table 39. Number and Percentage of Patients with TEAEs Navidea Biopharmaceuticals - Study No. NAV3-33 Safety Population (N=xxx)

Adverse Event Category ^a :	Overall (N=xxx)			
Total Number of TEAEs	XXX			
Patients with at Least One TEAE	xxx (xxx%)			
System Organ Class 1 Preferred Term 1	xxx (xxx%) xxx (xxx%)			
Preferred Term 2	xxx (xxx%)			
System Organ Class 2	xxx (xxx%)			
Preferred Term 1	xxx (xxx%)			
Preferred Term 2	xxx (xxx%)			

Table 40. Summary of TEAEs Navidea Biopharmaceuticals - Study No. NAV3-33 Safety Population (N=xxx)

	Overall
	(N=xxx)
Patients With at Least One TEAE	XXX
Maximum TEAE Severity Grade	
Mild	xxx (xxx%)
Moderate	xxx (xxx%)
Severe	xxx (xxx%)
Highest Relationship of TEAE to Tc 99m tilmanocept	
Definitely Not [n(%)]	xxx (xxx%)
Probably Not [n(%)]	xxx (xxx%)
Possibly [n(%)]	xxx (xxx%)
Probably [n(%)]	xxx (xxx%)
Definitely [n(%)]	xxx (xxx%)
Highest Relationship of TEAE to Study Procedure	
Definitely Not [n(%)]	xxx (xxx%)
Probably Not [n(%)]	xxx (xxx%)
Possibly [n(%)]	xxx (xxx%)
Probably [n(%)]	xxx (xxx%)
Definitely [n(%)]	xxx (xxx%)
Patients with at Least One TESAE	xxx (xxx%)

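### The added-value model represents the quantitative scan only by the yes/no bucketing result, so a significant combined-read term cannot tell new reader information from TUV information that the cut threw away

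*SAP*

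**What the plan says.** One secondary objective in SAP 1.0 (and Protocol 2.3) concerns this: "additive effect of either quantitative or qualitative assessment of Tc 99m tilmanocept imaging to the other at baseline and change from baseline". The later visit is Week 5, and the aim is prediction of response or non-response.

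SAP 4.2.3 says this "will be assessed with a generalized linear mixed model with the logit link function", with the patient's response status as outcome. On the fixed part it says: "Fixed model terms for the quantitative and qualitative plus quantitative assessments will be used". On the form of the quantitative term: "The quantitative assessment will be based on $\Delta TUV_{global[5w]}$ bucketing". On the random part: "Random terms will be fit for the subject and reader within subject using the variance component model".

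The Table 35 shell in SAP Appendix B describes each model term as an "Indicator variable for prediction of 'Improved' compared to the reference category" of no improvement, and its p-value as "Based on a two-sided t-test". Tables 35-36 apply the model at Week 12 and Tables 37-38 at Week 24, each in the ITD and PP populations.

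SAP 2.5 defines TUVglobal as a sum of fractional excesses over the normative mean and its change as a percentage, so both are continuous. SAP 4.1.1.1 then gives the bucketing rule: no improvement if baseline TUVglobal is below 5; otherwise improvement if the fall is at least 10%; otherwise no improvement. SAP 4.2.3 itself uses the continuous Week 5 change for the Kendall correlations, but not in this model.

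**The concern.** With a 0/1 covariate, falls of 11% and 70% are the same value for a patient with baseline of at least 5. So are a rise of 40% and a fall of 9%. If response depends on how large the change is, the bucketing term leaves real TUV information unexplained. The second term is a combined read of the same images that may depart from the bucketing call (Data Listing 29 exists to list such departures). If readers overturn calls partly because the change is marginal or very large, the read's coefficient picks up that leftover TUV information. The Type 3 test then comes out significant although, given the measured TUV, the read says nothing more about response.

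Tables 35-38 are the plan's only model-based answer to this objective. A small p-value there could be reported as a contribution of reader interpretation when it shows only that a binary summary is coarser than the measurement behind it.

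**Working it through.** **Inputs from the plan (SAP 1.3).** Assumed accuracy of bucketing at Week 24: specificity 0.92, sensitivity 0.80. Sizes: 98 non-responders and 100 responders (198), or 500 and 100 (600) if the 5:1 ratio holds.

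**Reproducing the plan's own figure.** Exact binomial test, one-sided 0.025:
- Specificity 0.80 v. 0.92, n = 98: reject at 87 or more correct. Size 0.0158, power 0.908.
- Sensitivity 0.65 v. 0.80, n = 100: reject at 75 or more correct. Size 0.0211, power 0.913.

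Both agree with the stated 90%, so the accuracy and sizes are a consistent starting point.

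**Assumptions not in the documents.** How closely the read follows continuous TUV; one record per patient in ordinary logistic regression; two-sided 0.05 as the rule for calling a term additive.

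**Set-up.** Marker X ~ N(0,1) in non-responders and N(d,1) in responders, with cut c.
- c = z(0.92) = 1.405
- d = z(0.92) + z(0.80) = 1.405 + 0.842 = 2.247
- Bucket: Q = 1 if X ≥ c. Read: V = 1 if X + noise ≥ c, so V has no link to response except through X.
- Likelihood-ratio test of V added to Q, compared with V added to X; 800 trials per setting.

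**Share of trials in which V tests as additive**

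| Noise (marker SD) | 198, beside Q | 600, beside Q |
|---|---|---|
| 0.25 | 56% | 81% |
| 0.5 | 69% | 89% |
| 1.0 | 58% | 84% |

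Repeat runs gave 56-70% at 198 and 79-90% at 600. With continuous X in the model, the rate is about 4-7% at both sizes.

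**How far this depends on the assumed read**
- Noise 0.1 SD: 26-34% at 198 and 53-54% at 600.
- Noise 1.5 SD: 45-47% and 66-67%.
- Read equal to the bucket flipped at random: 3-8%, near nominal.
- Accuracy at the null boundary (0.65 and 0.80), noise 0.25 to 1 SD: 31-61% beside Q, against 5-8% beside X.

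**Two-stage rule.** A single marker ignores the separate baseline cut of 5. A second simulation used independent baseline and change scores, each with its own cut, tuned to 0.80 and 0.92 (assumed proportion at or above the baseline cut: 0.50 of non-responders, 0.90 of responders). For noise 0.25, 0.5 and 1 SD, the read tested as additive in 64%, 76% and 72% at 198, and 90%, 95% and 93% at 600. With both continuous scores in place of the bucket the rate was 5-6%.

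**Three readers.** Pooled logistic regression with patient-clustered standard errors (reader correlation 0.7 and 0.9) gave 93-99% at 198 and 99.5-100% at 600; adding continuous TUV gave 4-7.5%. The literal mixed model could not be characterised: the outcome is identical on a patient's three records, and no likelihood maximum was found as the subject SD rose.

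**Which continuous form works.** Response was driven by the log ratio of Week 5 to baseline. Linear TUVglobal[b] and TUVglobal[5w] still let the read through in 9-30% of trials at 198 and 7-44% at 600 (250 runs per cell). Spline terms gave 4-10%, and baseline plus flexible percent change gave 4-8%. Two linear visit values are therefore not enough.

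**The case against.** Bucketing is the trial's pre-specified index test, and SAP 4.2.3 says that the quantitative assessment is based on it. Whether a read improves on that yes/no call is a fair clinical question, and the planned model addresses it. This stands, and is why the bucketing model should stay. But the objective speaks of quantitative assessment at baseline and in change, which also covers the measured values, and the planned model cannot answer that version.

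A reader might infer that the plan will wrongly declare the read additive in 55-90% of trials. The documents do not support that:
- They do not say how the combined read is formed, how often it departs from the bucket, or how closely it follows TUV. The rate runs from nominal to about 100% across plausible answers.
- The figures come from one-record-per-patient logistic regression, whereas the plan has three readers and random terms.
- Nothing is declared. The p-values are displayed, with no alpha or success rule for these tables, and formal testing covers only the co-primaries and the key secondary NPV.

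Tables 21-28 also report the accuracy of the qualitative and combined reads by reader, so the model is not the only evidence on the read. These points limit the size and consequence of the problem, but they do not remove the ambiguity in the term.

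**Conclusion.** The point holds as one of interpretation. With TUV present only as the bucketing result, a significant combined-read term has two explanations, new reader information or recovered TUV information, and Tables 35-38 cannot separate them.

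The size is illustrative: about 55-70% at 198 patients and 80-90% at 600 for a read with nothing beyond TUV, against about 4-7% with the correctly specified continuous marker. This rests on one reader, ordinary logistic regression, two-sided 0.05, the planned Week 24 accuracy, and reader noise of 0.25 to 1 SD. Only the accuracy and the sizes come from the plan. The percentages should not be quoted as error rates of the planned mixed model. Its random-effects structure is a separate matter. This is a secondary analysis, and the co-primary and key secondary tests are unaffected.

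**What to change.** In SAP 4.2.3 and Tables 35-38:

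1. Keep the bucketing model and label it as the answer to whether the read adds to the yes/no call.
2. Add a pre-specified model with continuous TUVglobal[b] and continuous percent change (or log ratio) to Week 5, using each reader's own values. Enter them through a restricted cubic spline with knots fixed in advance, not one that depends on a linearity test.
3. Test the read added to those terms, and those terms added to the read, by likelihood ratio.
4. State that a conclusion that the read adds to measured uptake will be drawn only from the continuous model.
5. Give a rule for zero values. Under SAP 2.5 TUVglobal is zero when no joint exceeds its limit; percent change is then undefined at a zero baseline, and the log ratio at a zero on either visit. The bucketing rule avoids this at baseline, but the continuous model will not.

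The cost is SAP wording, one further model and extra table rows, with no new data. The downside is a few extra degrees of freedom and a less simple odds ratio for the quantitative part.

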2.7 Documentation and Other Considerations

The data analyses will be conducted using SAS[®] Software, version 9.4 or later.

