4.1.1.2 Clinical Assessments

ACR Response is derived through a combination of reductions from baseline in swollen or tender joint counts as well as improvement from baseline in at least 3 of the other parameters (patient assessment, physician assessment, pain scale, disability/functionality questionnaire, and acute phase reactant [ESR]). This study will evaluate the following three levels of ACR Response:

• ACR20: An ACR20 indicates that 20% improvement is observed in tender and swollen joint counts as well as 20% improvement in at least 3 of the other 5 criteria.

- ACR50: An ACR50 indicates that 50% improvement is observed in tender and swollen joint counts as well as 50% improvement in at least 3 of the other 5 criteria.
- ACR70: An ACR70 indicates that 70% improvement is observed in tender and swollen joint counts as well as 70% improvement in at least 3 of the other 5 criteria.

Each patient will be classified as a yes or a no for whether they meet each of the above ACR Response Criteria at each of the applicable post-baseline time points. Note that the above criteria are nested, such that if a patient is a yes for ACR70 at a given time point, then the patient is also a yes for ACR50 and ACR20 for that same time point.

A patient will be classified as improved on the CDAI depending on the baseline score as follows:

- If the baseline value is greater than 22, a reduction of more than 12 will be classified as improved. Otherwise, the patient is not improved.
- If the baseline value is between 10 and 22 (inclusive) a decrease of more than 6 will classified as improved. Otherwise, the patient is not improved.
- If the baseline value is less than 10, a decrease of more than 1 will be classified as improved. Otherwise the patient is not improved.

A patient will be classified as improved on the DAS28 with a score change of greater than 1.2.

A decrease of at least 0.22 in the HAQ-DI will be classified as improved. Otherwise, the patient is not improved on the HAQ-DI.

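### The mixed model for what each read adds to the other gives a patient's three reader rows the same outcome, so its likelihood had no finite maximum in simulation at the plan's sizes, and it has no qualitative-only term

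*SAP*

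**What the plan says.** SAP section 4.2.3 plans a generalized linear mixed model with logit link for the added value of the reads.

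- **Outcome:** "The patient's response status will be used as the response variable". The clinical status is set per patient and visit in section 4.1.1.2: "Each patient will be classified as a yes or a no for whether they meet each of the above ACR Response Criteria".
- **Fixed terms:** "Fixed model terms for the quantitative and qualitative plus quantitative assessments will be used".
- **Random terms:** "Random terms will be fit for the subject and reader within subject using the variance component model".
- **Output:** "A table displaying the partial hypothesis tests (Type 3 test) for the fixed effects will be displayed".

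The footnote to the Table 35 shell in Appendix B repeats the model, with "fixed terms for quantitative and qualitative plus quantitative imaging assessment" and "random terms for subject and reader within subject using a variance component model". The shell has two rows: the quantitative read and the combined read. It is reused for Tables 36 to 38.

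Section 2.7 gives only the software ("The data analyses will be conducted using SAS"). Neither place names an estimation method or says what happens if the fit does not converge. The secondary objective in section 1.0 asks what each kind of read adds to the other.

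**The concern.** Section 1.2 has three readers, each giving a qualitative read and the regions of interest for TUV. A reader-within-subject term implies one row per reader, so each patient contributes three rows. The predictors can differ between these rows, but the outcome cannot.

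A random subject intercept describes correlation among outcomes that may differ within a patient. Here they never differ, so a very large intercept variance can explain each patient's outcome. Estimates and tests would then depend on where a particular algorithm stops.

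The second problem needs no calculation. Without a term for the qualitative read alone, one of the two directions in the objective has no test.

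At stake is whether Tables 35 to 38 can answer that objective.

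**Working it through.** **1. Sizes.** The documents give no figure for this model, so the check uses the sizes in SAP section 1.3. Each is an exact binomial test at one-sided 0.025: the smallest c with P(X ≥ c | n, p0) ≤ 0.025, and power P(X ≥ c | n, p1).

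- Specificity, n = 98, 0.80 against 0.92: c = 87, alpha 0.0158, power 0.908.
- Sensitivity, n = 100, 0.65 against 0.80: c = 75, alpha 0.0211, power 0.913.

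Both reproduce the stated 90%. At the plan's 5:1 ratio, 100 responders go with 500 non-responders. The two sizes are written 100/98 and 100/500 below.

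**2. Why the likelihood can keep rising.** Leave out the reader term for now. For patient i with reader rows j, the contribution is

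∫ Π_j p_ij^{y_i} (1 − p_ij)^{1−y_i} φ(u) du, with logit p_ij = x_ij′β + σu.

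The outcome y_i has no index j. Put β = σb and let σ grow. A responder's contribution tends to Φ(min_j x_ij′b) and a non-responder's to Φ(−max_j x_ij′b). The log-likelihood thus has a finite limit at infinite σ, with coefficients proportional to σ. The question is whether any finite σ does better.

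**3. Simulation inputs.**

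- Quantitative reads: sensitivity 0.80, specificity 0.92, between-reader correlation 0.7 through a Gaussian copula (SAP section 1.3).
- Qualitative reads (assumed): sensitivity/specificity 0.60/0.70, 0.70/0.80, 0.80/0.92 or 0.90/0.97, with the same correlation.
- Combined read (assumed): takes the qualitative result in 10%, 30% or 50% of reads.
- Five datasets per setting and size: 4 × 3 × 2 × 5 = 120. Sixty more had the two reads correlated 0.5 given status, replacement by patient, or reader correlation 0.9.

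The subject intercept was integrated on a fine grid and the fixed effects were re-maximised at each subject SD.

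**4. Results.** The log-likelihood rose at every step in 120 of 120 and in 60 of 60. Two examples with 30% replacement:

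| Subject SD | 100/500, qualitative 0.70/0.80 | 100/98, qualitative 0.90/0.97 |
|---|---|---|
| 0 | -488.5 | -217.6 |
| 1 | -415.0 | -190.4 |
| 3 | -304.1 | -147.2 |
| 10 | -245.7 | -121.5 |
| 30 | -228.8 | -113.8 |
| 100 | -223.1 | -111.1 |

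The gains from SD 0 to 100 are 488.5 − 223.1 = 265.4 and 217.6 − 111.1 = 106.5.

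In all 120, the larger fixed coefficient at SD 100 was 73 to 152, which was 3.2 to 3.5 times its value at SD 30. The SDs themselves have ratio 100/30 = 3.33. Which coefficient runs away depends on the assumptions. At 100/500, from SD 0 to 100:

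- 0.70/0.80: quantitative 2.9 to 134.7, combined 1.1 to 2.2.
- 0.90/0.97: quantitative 1.3 to 58.0, combined 3.0 to 95.5.

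**5. Could there be a later maximum?** Four further datasets followed to SD 200 kept rising. One (100/500, 0.70/0.80) went from -413.2 at SD 0 to -203.7 at 100 and -202.7 at 200, against the step 2 limit of -201.7. Separate code, with other rules for the combined read and correlations from 0 to 0.9, gave a rise at every step to SD 40 in 224 of 224 datasets.

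**6. Reader-within-subject term.** Each level has one binary row. At 100/500 and subject SD 10, the log-likelihood was -239.3, -250.4 and -260.1 at reader SD 0, 2 and 3. At subject SD 0 it was flat in the reader SD (within 0.02). The term is redundant.

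**7. Dependence on the method** (own code, not SAS; 18 datasets).

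- Pseudo-likelihood settled at subject variance 3.7 to 4.5, with reader variance 0.
- Laplace and 9-point adaptive quadrature stopped at subject SD 54 or more in all 18.
- On one 100/98 dataset the combined coefficient was 1.10, 12.3 and -12.1 under the three methods.
- A separately written pseudo-likelihood fit, one dataset per size, gave subject variance 4.6 at 100/98 and 0 at 100/500.

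The test is also sensitive to the SD. The combined term's z exceeded 1.96 in 19, 29, 30 and 30 of 30 datasets at SD 0 (the four accuracies in order), and in 0, 0, 10 and 23 at SD 100. These are z-values at fixed SDs, not predictions of what software would print.

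**8. Missing direction.** In the planned model, the combined term given the quantitative term asks what the combined read adds to the quantitative read. The quantitative term given the combined term asks what the quantitative read adds to a read that already contains it. Neither asks what it adds to the qualitative read.

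**The case against.** The SAP does not say maximum likelihood. Under pseudo-likelihood the planned model can be fitted. A separate check with the subject term only converged in all 1,200 null datasets and in all 1,440 datasets over the accuracy grid above. It gave no false positives for the combined term in the 1,200. On that view the defect is an unnamed method and a conservative test; power was 0 to 12% at 100/98 with 10% replacement and the two lower accuracies. This stands as a limit on the claim: finite output can be produced. It is no defence of the plan, because the method is not specified and the values do not maximise the likelihood. In the 100/500 example, pseudo-likelihood stops at SD 2.1, while the exact log-likelihood still rises from -304.1 at SD 3 to -223.1 at SD 100.

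A rise to the last grid point does not by itself exclude a later maximum. The runs to SD 200 and the infinite-SD limit answer this for the datasets examined, but they are not a general proof.

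The three-method comparison of coefficients is one dataset, and logit coefficients scale with the subject SD, so their sizes are not comparable. That is accepted.

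Tables 21 to 28 show the qualitative and combined reads by reader, so a descriptive comparison remains. What is missing is a test.

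Finally, Data Listing 29 treats the combined read as an assessment in its own right, and a model with two separate indicators does not evaluate it. It should therefore stay in Tables 25 to 28.

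**Conclusion.** The model is wrong as written and should be changed. Two facts follow from the text alone: the outcome is constant across a patient's reader rows, and there is no qualitative-only term. The absence of a finite likelihood maximum is a simulation result: 180 of 180 datasets at the plan's sizes, supported by separate code. It rests on the plan's accuracy and correlation for the quantitative read, and on assumed values for the qualitative read and for how the combined read is formed. The rise held in every setting tried. Which coefficient diverges, and whether the combined term stays significant, did depend on those assumptions.

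The reach is limited to Tables 35 to 38. The additive effect is a stated objective but not a listed secondary endpoint. The exact tests for the co-primary and key secondary endpoints are not affected.

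**What to change.** - Drop both random terms.
- Fit one logistic regression per reader, one row per patient, with clinical response as outcome and separate indicators for the quantitative (bucketing) read and the qualitative read. Report each 1-df test given the other, which covers both directions of the objective.
- Use Firth's penalised likelihood with penalised likelihood-ratio tests. Plain maximum likelihood can separate when the qualitative read is very accurate.
- If a pooled result is wanted, use a GEE logistic model with independence working correlation and robust variance clustered on patient. State in advance that it will be reported as not estimable if the estimates are not finite.
- Keep the combined read in Tables 25 to 28.

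The check used 4 accuracies × 3 settings × 5 datasets × 3 readers = 180 fits per size. Plain fits were finite in 178 of 180 at 100/500 and 164 of 180 at 100/98 (30 of 45 at 0.90/0.97). Firth fits were finite in 360 of 360. The pooled GEE was finite in 60 of 60 and 58 of 60. These counts show only that the fits exist; they say nothing about power or error rates.

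The cost is SAP wording in section 4.2.3 and revised shells for Tables 35 to 38. No new data are needed.
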